9.1.8. Electrocardiogram

A triplicate 12-lead ECG will be recorded at baseline; thereafter, single 12-lead ECGs will be recorded. Additional ECGs may be collected at the discretion of the Investigator. Standard computerized 12-lead electrocardiogram (ECG) recordings will be obtained. Each lead shall be recorded for at least 3 beats at a speed of 25 mm/s. Recordings will be obtained before dosing, after the patient has rested comfortably for approximately 10 minutes. The electrophysiological parameters assessed will be rhythm, ventricular rate, PR interval, QRS duration, QT interval, ST and T-waves, Bazett-corrected QT interval (QTcB) and Fredericia-corrected QT interval (QTcF).

When an ECG is scheduled at the same time as a blood sample collection, the ECG will be obtained before the scheduled blood sample.

The Investigator or designee is responsible for reviewing the ECGs to assess whether the results have changed since the Screening/Baseline visit and to determine the clinical significance of the results. These assessments will be recorded on the eCRF. For any clinically significant changes from the Screening/Baseline visit (eg, ischemic ECG changes, wave/interval changes, or arrhythmia), the Investigator must contact the CRO Medical Monitor to discuss continued participation of the patient in the study.

9.1.9. Laboratory Assessments

The following clinical laboratory tests will be evaluated by a central laboratory. In the event of an unexplained clinically relevant abnormal laboratory test occurring after study drug administration, the test should be repeated and followed up at the discretion of the Investigator until it has returned to the normal range or stabilized, and/or a diagnosis is made to adequately explain the abnormality.

Hematology	
Hematocrit	Neutrophils, absolute and %
Hemoglobin	Lymphocytes, absolute and %
RBC count	Monocytes, absolute and %
WBC count	Eosinophils, absolute and %
Mean corpuscular volume	Basophils, absolute and %

Mean corpuscular hemoglobin	Platelet count
Mean corpuscular hemoglobin concentration	
Serum Chemistry	
Sodium	Potassium
BUN	Phosphate
Creatinine ^a	Albumin
Uric acid	Calcium
LDH	Carbon dioxide
Glucose	Chloride
Liver Function Tests	
AST	ALP
ALT	Bilirubin (total and direct)
Coagulation Assessments	
PT	INR
aPTT	
Thyroid Function Test	
TSH	
Serology Parameters	
HBsAg	HBsAb
HCV Ab	
Urinalysis	
Visual inspection for appearance and color	Bilirubin
pH (dipstick)	Nitrite
Specific gravity	RBCs
Ketones	Urobilinogen
Albumin	Leukocytes
Glucose	Microscopy (if clinically indicated)
Pregnancy Testing (WOCBP only)	
β-human chorionic gonadotropin	
Other	
Vitamin A	Vitamin B12
Abbreviations: AST=aspartate transaminase; ALP=alkalin urea nitrogen; HBsAg=hepatitis B surface antigen; HBsA	he phosphatase; ALT=alanine transaminase; BUN=blood Ab=hepatitis B surface antibodies; HCVAb=antihepatitis

urea nitrogen; HBsAg=hepatitis B surface antigen; HBsAb=hepatitis B surface antibodies; HCVAb=antihepatitis C virus antibodies; INR=international normalized ratio; LDH=lactate dehydrogenase; PT=prothrombin time; aPTT=activated partial prothrombin time; RBC=red blood cells; TSH=thyroid stimulating hormone; WBC=white blood cell; WOCBP=women of child bearing potential.

^a eGFR will be calculated by a central laboratory using the Modification of Diet in Renal Disease formula, where eGFR in mL/min/1.73m² = $175 \times [\text{serum creatinine in mg/dL}^{-1.154}] \times [\text{Age}^{-0.203}] \times [1.212 \text{ if Black}] \times [0.742 \text{ if female}].$

9.1.9.1. Pregnancy Screening

A serum pregnancy test will be performed for WOCBP at screening. A urinary pregnancy test will be performed monthly and at any time pregnancy is suspected. The results of the pregnancy test must be known before administration of study drug. Patients who are pregnant are not eligible for study participation. Patients determined to be pregnant while on study will be followed until the pregnancy outcome is known (Section 9.8).

9.1.9.2. Exploratory Biomarkers

Where local regulations permit, predose blood samples will be collected. Collection of blood samples for long-term storage to permit testing of additional proteins related to FAP and exploratory biomarker analysis will be subject to discretionary approval from the IRB/IEC at the clinical study centers. Samples will be stored by the Sponsor or designee in a secure and controlled environment until analysis, and will be destroyed by the Sponsor or designee after all worldwide obligations have been met, or sooner if required by local regulations.

9.1.9.3. Antidrug Antibodies

Blood samples will be collected to evaluate antidrug antibodies. Blood samples for antidrug antibody testing must be collected before study drug administration.

9.2. Adverse and Serious Adverse Events

9.2.1. Definition of Adverse Events

9.2.1.1. Adverse Event

An AE is defined as any unfavorable and unintended change in structure, function, or chemistry of the body temporally associated with the use of the investigational product, whether or not it is considered related to the use of the product.

Any medical condition that is present when a patient is screened and does not deteriorate should not be reported as an AE; however, if the medical condition does deteriorate at any time after administration of the first dose of study drug, it should be reported as an AE.

9.2.1.2. Serious Adverse Event

An SAE is any untoward medical occurrence that at any dose:

- Results in death
- Is life-threatening (an event which places the patient at immediate risk of death from the event as it occurred. It does not include an event that had it occurred in a more severe form might have caused death)
- Requires in-patient hospitalization or prolongation of existing hospitalization
- Results in persistent or significant disability or incapacity

- Is a congenital abnormality or birth defect
- An important medical event that may not be immediately life-threatening or result in death or hospitalization but may jeopardize the patient and may require intervention to prevent one of the other outcomes listed in the definition above (eg, events include allergic bronchospasm requiring intensive treatment in an emergency room or at home, blood dyscrasias, convulsions, or the development of drug dependency or abuse)

9.2.1.3. Adverse Events of Clinical Interest

The following events are considered to be AEs of clinical interest:

- ISRs
- Hepatic AEs, including LFT abnormalities considered clinically significant by the Investigator

9.2.2. Eliciting Adverse Event Information

The patient should be asked about medically relevant changes in his/her health since the last visit. The patient should also be asked if he/she has been hospitalized, had any accidents, used any new medications, or changed concomitant medication routines (both prescription and OTC). In addition to patient observations, AEs will be documented from any clinically relevant laboratory findings, physical examination findings, ECG changes, or other findings that are relevant to patient safety.

9.3. Adverse Event Reporting

The Investigator is responsible for reporting all AEs that are observed or reported after administration of the first dose of study drug regardless of their relationship to study drug through the end of study (28 days after administration of the last dose of study drug).

All AEs must be recorded in the source records for the clinical study center and in the eCRF for the patient, whether or not they are considered to be drug-related. Each AE must be described in detail: onset time and date, description of event, severity, relationship to investigational product, action taken, and outcome (including time and date of resolution, if applicable).

For AEs that are considered AEs of clinical interest, additional clinical information may be collected based upon the severity or nature of the event.

If a patient has ISRs meeting any of the following criteria, the Investigator or delegate should contact the Medical Monitor and submit a supplemental ISR eCRF:

- ISRs that are recurrent and/or demonstrate a pattern of increasing severity
- Any ISR that is determined to be severe and/or a cause for study drug discontinuation
- Any ISR which, in the opinion of the Investigator, requires further medical evaluation or treatment

In some cases, where it is medically appropriate, further evaluation may include photographs, referral to a dermatologist, skin biopsy, or other laboratory testing. If a biopsy was obtained, the

Sponsor may request that the biopsy also be reviewed by a central dermatopathologist. To better understand the safety profile of the study drug, additional analysis of biopsy tissue may be performed according to local regulations.

For patients with hepatic AEs, additional information, including, clinical history, course of event, and local laboratory results to monitor LFT levels or other laboratory parameters, may be collected.

9.4. Assessment of Causality

Causal relationship assessment to drug treatments is required for purposes of reporting AEs. To promote consistency, the following guidelines should be taken into consideration along with good clinical and scientific judgment when determining the relationship of drug treatments to an AE:

Definitely Related:	A clinical event, including laboratory test abnormality, occurring in a plausible time relationship to the medication administration, and which cannot be explained by concurrent disease or other drugs or chemicals. The response to withdrawal of the drug should be clinically plausible.	
Possibly Related:	A clinical event, including laboratory test abnormality, with a reasonable time sequence to the medication administration, but which could also be explained by concurrent disease or other drugs or chemicals. Information on the drug withdrawal may be lacking or unclear.	
Unlikely Related:	Related: A clinical event, including laboratory test abnormality, with little or no tempo relationship to medication administration, and which other drugs, chemicals, ounderlying disease provide plausible explanations.	
Not Related:	A clinical event, including laboratory test abnormality that has no temporal relationship to the medication or has more likely alternative etiology.	

9.5. Assessment of Severity

Adverse events are to be graded according to the categories detailed below:

Mild	Mild events are those which are easily tolerated with no disruption of normal daily activity.	
Moderate	Moderate events are those which cause sufficient discomfort to interfere with normal daily activities.	
Severe	Severe events are those which incapacitate and prevent usual activity.	

Changes in severity should be documented in the medical record to allow assessment of the duration of the event at each level of severity. Adverse events characterized as intermittent require documentation of the start and stop of each incidence. When changes in the severity of an AE occur more frequently than once a day, the maximum severity for the experience that day should be noted. If the severity category changes over a number of days, then those changes should be recorded separately (with distinct onset dates).

9.6. Coding of Adverse Events

The Medical Dictionary of Regulatory Activities (MedDRA) will be used to code AEs.

9.7. Serious Adverse Event Reporting

An assessment of the seriousness of each AE will be made by the Investigator. Any AE and laboratory abnormality that meets the SAE criteria in Section 9.2.1.2 must be reported to the CRO within 24 hours from the time that clinical study center staff first learns of the event. All SAEs must be reported regardless of the relationship to study drug.

The initial report should include at least the following information:

- Patient's study number
- Description and date of onset of the event
- Criterion for serious, and
- Preliminary assignment of causality to study drug

To report the SAE, complete the SAE form. Within 24 hours of receipt of follow-up information, the Investigator must update the SAE form. SAEs must be reported using the contact information provided below.

SAE Reporting Contact Information Medpace, Inc. [contact] Country-specific fax numbers will be included in the Study Reference Manual

Appropriate remedial measures should be taken by the Investigator using his/her best medical judgment to treat the SAE. These measures and the patient's response to these measures should be recorded. All SAEs, regardless of relationship to study drug, will be followed by the Investigator until satisfactory resolution or the Investigator deems the SAE to be chronic or stable. Clinical, laboratory, and diagnostic measures should be employed by the Investigator as needed to adequately determine the etiology of the event.

9.7.1. Notifying the Institutional Review Board/Independent Ethics Committee

Serious adverse events will be reported to the IRB/IEC per their institutional policy by the Investigator or Sponsor (or Sponsor designee) according to country requirements. Copies of each report and documentation of IRB/IEC notification and acknowledgement of receipt will be kept in the Investigator's study file.

9.7.2. Sponsor Reporting: Notifying Regulatory Authorities

The Sponsor or its representative is required to report certain study events in an expedited manner to the Food and Drug Administration, the European Medicines Agency's EudraVigilance electronic system according to Directive 2001/20/EC, and to all country Regulatory Authorities where the study is being conducted, according to local applicable regulations.

The following describes the safety reporting timeline requirements for suspected unexpected serious adverse reactions and other reportable events:

Immediately and within 7 calendar days

• Any suspected adverse reaction that is: associated with the use of the study drug, unexpected, and fatal or life threatening. Follow-up information must be reported in the following 8 days.

Immediately and within 15 calendar days

- Any suspected adverse reaction that is: associated with the use of the study drug, unexpected, and serious, but not fatal or life threatening, and there is evidence to suggest a causal relationship between the study drug and the reaction.
- Any finding from tests in laboratory animals that: suggest a significant risk for human patients including reports of mutagenicity, teratogenicity, or carcinogenicity.
- Any event in connection with the conduct of the study or the development of the study drug that may affect the safety of the trial patients.

In addition, periodic safety reporting to regulatory authorities will be done by the Sponsor or its representative according to national and local regulations.

9.7.3. Sponsor Notification of Participating Investigators

All Investigators will be informed by the Sponsor or its representative of relevant clinical safety findings from this or other clinical studies, as well as any new findings from tests in laboratory animals that significantly impact the benefit/risk to patients in this study. All reports should be transmitted to the IEC/IRB that approved the study.

9.8. **Pregnancy Reporting**

A female patient with a positive pregnancy test at screening is ineligible for this study. If a female patient becomes pregnant during the course of this study (or during the first month following the last dose of study drug), the patient must be instructed to stop all study drug administration, and the Investigator must report the pregnancy to the CRO within 24 hours of being notified of the pregnancy. Details of the pregnancy will be recorded on the pregnancy reporting form. The patient should receive any necessary counseling regarding the risks of continuing the pregnancy and the possible effects on the fetus.

The pregnancy should be followed by the Investigator until completion. At the completion of the pregnancy, the Investigator will document the outcome of the pregnancy. If the outcome of the pregnancy meets the criteria for an SAE (ie, postpartum complication, spontaneous abortion, stillbirth, neonatal death, or congenital anomaly), then the Investigator should follow the procedures for reporting an SAE as outlined in Section 9.7.

If the female partner of a patient becomes pregnant during the course of this study, the Investigator must report the pregnancy to the CRO within 24 hours of being notified of the pregnancy. The pregnancy should be followed by the Investigator until its conclusion.

10. STATISTICS

10.1. Sample Size

This is an open-label study to evaluate efficacy, safety, and PK of revusiran in patients with TTR-mediated FAP with disease progression post-OLT. In healthy volunteers, mean reduction of 88% in serum TTR has been observed from baseline to Day 35 with a standard deviation of 6%. If this study yields a mean reduction of 80% at 6 months with a standard deviation of 6%, 12 patients would yield a 95% confidence interval (CI) of approximately 77% to 83%.

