3.2. Number of Patients

Approximately 12 patients are planned for enrollment in this study.

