4.4. Withdrawal Criteria

While patients who discontinue drug are encouraged to remain in the study to complete study assessments (Section 4.3), they are free to withdraw from the study at any time and for any reason, without penalty to their continuing medical care. Patients who withdraw or have a dose reduction before 6 months of study participation may be replaced. Patients will also be withdrawn if the study is terminated.

If a patient chooses to withdraw from the study, every effort should be made to conduct the Early Termination visit. When a patient withdraws from the study, the primary reason for discontinuation must be recorded in the appropriate section of the electronic case report form (eCRF) and all efforts will be made to complete and report the observations as thoroughly as possible.

The withdrawn patient will be asked to consent to either be contacted by telephone or to allow nonpatient contact follow-up (eg, medical record check) for up to 18 months after enrolling onto the study to document their overall health status.

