10.2.1. Populations to be Analyzed

The populations (analysis sets) are defined as follows:

Evaluable Analysis Set: All patients who have received at least one dose of study drug and have a non-missing serum TTR result at the Month 6 (Week 26) visit.

Safety Analysis Set: All patients who received at least a single dose of study drug.

PK Analysis Set: All patients who received at least a single dose of study drug and have at least 1 postdose blood sample for PK parameters and who have evaluable PK data.

The primary population used to evaluate efficacy will be the Evaluable Analysis Set. Safety will be analyzed using the Safety Analysis Set. The PK Analysis Set will be used to conduct PK analyses.

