10.2.3. Efficacy Analyses

10.2.3.1. Primary Efficacy Endpoint

The primary efficacy endpoint is the percent reduction from baseline in serum TTR level at 6 months. This analysis will be a 2-sided 95% CI for the mean of the primary endpoint. A t-test,

in which the null hypothesis of no reduction is compared against the alternative hypothesis of a change, will also be performed.

Sensitivity analyses, including different methods for handling the missing data, will assess the robustness of the primary endpoint for the Evaluable Analysis Set.

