### 3.9. Withdrawals, Dropouts, Loss to Follow-up

Patients who withdraw before month 6 or have a dose reduction before 6 months of study participation may be replaced.

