### 3.10. Missing Data

In general, there will be no substitutions made to accommodate missing data points. All data recorded on the electronic case report form (eCRF) will be included in data listings that will accompany the CSR. Data collected at multiple time points throughout the study will be presented in chronological order in the data listings according to assessment date/time. Data summaries and analyses will be based on observed data only.

Methods for handling incomplete or missing components of efficacy endpoints are discussed in the endpoint scoring algorithms in Section 6.

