### 4.3. Efficacy Analysis

#### 4.3.1. Primary Efficacy Endpoint

The primary efficacy analysis will be performed after all patients have finished 6 months of treatment with study drug. The primary efficacy analysis will be based on the Evaluable Analysis Set.

The primary efficacy endpoint is the percent change from baseline in serum TTR level at 6 months. The mean percent change in serum TTR from baseline to 6 months with the associated 95% CI will be presented. A 2-sided 80% CI will also be generated. A t-test of the null hypothesis of no change in serum TTR from baseline at 6 months will be performed at the 2-sided, 0.05 confidence level.

Sensitivity analyses will be conducted to assess the robustness of the primary analysis. The sensitivity analyses will include a bootstrap 95% CI for the median percent change from baseline to 6 months in serum TTR. The bootstrap CI will be constructed using the percentile method. That is, the lower and upper limits of the bootstrap CI are defined as the 2.5th and 97.5th percentiles of the median percent change from baseline estimated from 1000 bootstrap samples. In addition to the t-test described above, a sensitivity analysis will include the p-value from the Wilcoxon signed rank test.

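### The stated precision for 12 patients (95% CI about 77% to 83%) rests on a large-sample quantile; the interval that matches the planned t-test is about 76% to 84%, and it applies to evaluable rather than enrolled patients

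*Protocol*

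**What the plan says.** The sample size rests on a precision statement, not on power. Protocol 10.1 starts from healthy-volunteer data at Day 35 (mean reduction 88%, SD 6%). It then supposes a mean reduction of 80% with an SD of 6% at 6 months and concludes that "12 patients would yield a 95% confidence interval (CI) of approximately 77% to 83" percent. Protocol 1.3 and SAP 3.1 repeat the figure. None of the three places says which quantile was used.

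For the primary endpoint, Protocol 10.2.3.1 says "This analysis will be a 2-sided 95% CI for the mean of the primary endpoint" and adds a t-test. SAP 4.3.1 keeps the pairing: "A t-test of the null hypothesis of no change in serum TTR from baseline at 6 months will be performed", two-sided at 0.05. SAP 4.3.1 gives the method for the bootstrap sensitivity interval (percentile method, 1000 samples) but none for the primary interval.

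On numbers, Protocol 3.2 says "Approximately 12 patients are planned for enrollment in this study". The primary analysis uses the Evaluable Analysis Set, whose members must "have a non-missing serum TTR result at the Month 6 (Week 26) visit" (Protocol 10.2.1). Under SAP 3.10, "Data summaries and analyses will be based on observed data only". Protocol 4.4 provides that "Patients who withdraw or have a dose reduction before 6 months of study participation may be replaced", and SAP 3.9 carries the same option.

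**The concern.** With 12 observations and an SD estimated from those same observations, a CI for the mean that agrees with a one-sample t-test uses the t quantile on 11 degrees of freedom. The printed interval looked too narrow for that. This is the only quantitative support for n = 12 and it appears three times, so the figure should be the one the planned analysis would give under the stated assumptions.

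The second question is which 12 patients are meant. The interval will be computed on patients with a Month 6 result, while 12 is the planned enrolment and no allowance for loss is stated.

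Little is at stake: the reported precision of the estimate, not a decision or a test result.

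**Working it through.** **Inputs.** Mean reduction 80%, SD 6%, n = 12 (Protocol 1.3 and 10.1, SAP 3.1). Two-sided 95% CI for the mean, with a t-test (Protocol 10.2.3.1, SAP 4.3.1).

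**Standard error.** SD/√n = 6/√12 = 1.732.

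**The plan's own figure.** With the normal quantile, 1.960 × 1.732 = 3.395. The interval is 80 ± 3.39 = 76.61 to 83.39, which rounds to 77% to 83% as printed. The rough rule of 2 standard errors gives 80 ± 3.46 = 76.54 to 83.46 and rounds the same way, but it too is a large-sample approximation.

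**The interval that matches the t-test.** t(0.975; 11 df) = 2.201, and 2.201 × 1.732 = 3.812. The interval is 80 ± 3.81 = 76.19 to 83.81, which rounds to 76% to 84%.

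**Size of the difference.** 3.812/3.395 = 1.123, so the half-width is 12% larger. 3.812 − 3.395 = 0.417 percentage points per limit. Both limits change at whole-percent rounding.

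**Dependence on the evaluable number.** The documents give no dropout rate, so the values of n other than 12 are assumptions for illustration. t-based, SD 6%:

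| Evaluable n | t quantile | Half-width | 95% CI |
|---|---|---|---|
| 8 | 2.365 | 5.02 | 75.0 to 85.0 |
| 9 | 2.306 | 4.61 | 75.4 to 84.6 |
| 10 | 2.262 | 4.29 | 75.7 to 84.3 |
| 11 | 2.228 | 4.03 | 76.0 to 84.0 |
| 12 | 2.201 | 3.81 | 76.2 to 83.8 |
| 13 | 2.179 | 3.63 | 76.4 to 83.6 |
| 14 | 2.160 | 3.46 | 76.5 to 83.5 |

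**What it would take to support the printed figure.** To round to 77% to 83%, the half-width must be about 3.5 or less. At SD 6% that needs 14 evaluable patients. At n = 12 it needs an SD of at most 3.5 × √12 / 2.201 = 5.51%.

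**Effect on the test.** Against no change, t = 80/1.732 = 46.2. The choice of quantile makes no difference to the result.

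**Can the evaluable number differ from 12?** It can go either way. Replacement is optional and is triggered by withdrawal or dose reduction; a missed Month 6 sample in a patient who stays on study does not trigger it. Conversely, a replaced patient who still has a Month 6 TTR result meets the definition of the Evaluable Analysis Set and stays in it, so the number can also exceed 12.

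**The case against.** The strongest reply is that no arithmetic slip has been made. The printed interval reproduces with 1.96, the text calls it approximate, neither document says the planning interval is t-based, and a normal approximation is a common planning shortcut. That is fair as an account of where the figure came from. It does not make the figure right for this plan: the analysis is a mean with a t-test in about 12 patients, and both limits move at the precision the sponsor chose to print.

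A second reply is that the inputs are looser than the correction. The 6% is a rounded value from healthy volunteers at Day 35; letting the SD run from 5.5% to 6.5% moves the t half-width at n = 12 from 3.49 to 4.13. This is true of how well the SD is known, but the sentence is conditional on an SD of 6%, and under that condition the matching interval is 76.2 to 83.8.

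On evaluable against enrolled patients, the objection has more force. Besides replacement, Protocol 4.3 encourages patients who stop study drug to stay for assessments, and SAP 3.11 tabulates data under the visit recorded on the eCRF even outside the window, so a late sample can still count as Month 6. These provisions make losses less likely without guaranteeing 12 results. Since the number may also exceed 12, this part shows that the sentence is unclear about which patients it counts, not that it is biased in one direction.

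Finally, nothing depends on the width: there is no success threshold on it, no prespecified stopping rule and no formal interim analysis. That stands, and it limits the weight of the point.

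**Conclusion.** The figure is wrong as written for the analysis that is planned, and the error is minor. Under the plan's own assumptions (mean 80%, SD 6%, 12 patients contributing data), the t-based 95% CI is 76.2% to 83.8%, about 76% to 84%. The printed 77% to 83% understates the half-width, which should be 12% larger. The conclusion rests on one inference: that the primary CI is the t interval corresponding to the planned t-test, since the documents do not name the CI method. The evaluable-versus-enrolled point is secondary; it is softened by the replacement option and has no fixed direction.

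**What to change.** In SAP 3.1, restate the precision along these lines: with 12 evaluable patients, a mean reduction of 80% and an SD of 6%, the t-based 95% CI for the mean is about 76% to 84%. Make the same change in Protocol 1.3 and 10.1 at the next amendment. In SAP 4.3.1, add that the 95% CI for the mean is based on the t distribution; this fills in a missing detail and is secondary to correcting the number.

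The cost is a few words and a slightly less favourable precision figure. Enrolment and the planned analyses stay as they are. Because Protocol 11.4 requires protocol amendments to be submitted to the IRB or IEC and the regulatory authority for approval, the SAP can be corrected first and the protocol text need not prompt an amendment of its own.
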